6.4 Study Assessments by Visit

Screening Prior to Baseline:

- 1) Eligible patients at the UCSF Mission Bay, Parnassus, and Zuckerberg San Francisco General Hospital sites will be identified through a medical records query and sent an email through MyChart to participate in the study. Patients who are interested will e-confirm their interest.
- 2) Research staff will reach out to interested patients and conduct a telephone screening call to determine eligibility.
- 3) Study visits and procedures will be described and eligible persons will be invited to attend the baseline visit.

Baseline (Orientation) Visit

Consented participants who completed the appropriate assessments prior to baseline will complete the following procedures at the baseline visit:

- 1) If an in-person baseline visit is not feasible, it will be held remotely over a Zoom Conference.
- 2) Study coordinators will obtain written informed consent from eligible participants.
- 3) Participants will be asked to complete a self-administered questionnaire. A complete medical history will be ascertained, including smoking and alcohol use.
- 4) We will also be measuring patient attitudes toward deprescribing using questionnaires including the Revised Patients' Attitudes Towards Deprescribing (rPATD), Voils Dose-nonadherence measure, and satisfaction with tamsulosin.
- 5) At the end of the orientation visit, research staff will provide verbal and written instructions for the study. Research staff contact information will be provided for reporting severe or concerning symptoms for the duration of the study.

End of study remote visit

- 1) After finishing the 12 weeks of the study, participants will be contacted by telephone to assess adherence to the program via phone and complete a follow-up questionnaire.
- 2) Participants will be asked to complete self-administered questionnaires via REDCap. These will include the same questionnaires measuring patient attitudes toward deprescribing using tools

PERSONAL Page 16 of 30

Protocol Version Number: 1.0

Protocol Version Date: 01/20/2023

including the Revised Patients' Attitudes Towards Deprescribing (rPATD), Voils Dosenonadherence measure, and satisfaction with tamsulosin.

3) A study clinician will review the patients' individual results with them in detail.

PERSONAL Page 17 of 30

7.0 Intervention Period

7.1 Intervention

All N-of-1 trials will have a duration of 12 weeks during which participants will complete the runin and 2 cycles consisting of a pair of 2-week treatment periods (taking tamsulosin or placebo) separated by 1 week of wash-out on placebo. The order of treatment periods within a cycle will be random (e.g. ABAB, BABA, ABBA, or BAAB).

Participants will receive a bubble pack with 11 weeks of tamsulosin (at their previously prescribed dose) or matching placebo and will be instructed to start taking the study medications after successfully completing the 1-week run-in period.

Participants will start with a 1-week open label run-in period where they will use the daily symptom questionnaires, accessible via smartphone or computer to track daily symptoms and side effects while not taking their tamsulosin or any study pills. Participants will receive a placebo during washout periods between treatment periods and cycles, but they will be unaware of the order or duration of treatment periods or cycles to prevent self-correlating symptoms to specific treatments.

The PERSONAL REDCap project will present participants with a daily questionnaire, accessible via smartphone, to track their symptoms. We chose to track the severity of lower urinary tract symptoms (LUTS) using a modified version of the widely used Urological Association Symptom Index (AUASI). This modified questionnaire includes daily questions regarding storage and voiding symptoms. All participants will also be presented a global urinary symptom bother question. Medication adherence, global urinary satisfaction questions, and health-related quality of life will be assessed as baseline and at the end of the study.

Participants will view a graphical representation of their responses during tamsulosin and placebo treatment at the end of the study. To maximize adherence to daily questionnaires, participants will be contacted via email or phone if they do not complete the daily symptom questionnaire for more than 3 consecutive days during their N-of-1 trial. Then, a PERSONAL clinician will review N-of-1 trial results with the participant.

8.0 ENDPOINTS

Aim 1: To determine if placebo-controlled N-of-1 deprescribing trials can identify older men who are likely to benefit from stopping ineffective chronic tamsulosin therapy for LUTS

 change in urinary symptoms measured with the IPSS score between treatment with tamsulosin and placebo

Aim 2: To describe the recruitment timeframe, study retention, and questionnaire completion rates.

- recruitment timeframe (months)
- study completion rate (goal >70% of participants)
- questionnaire completion rate (% completing >50% of daily questionnaires)

Aim 3: To describe patient characteristics at baseline related to the condition and their medication

PERSONAL Page 18 of 30

- urinary bother
- Tamsulosin satisfaction
- Tamsulosin adherence
- patient attitudes towards deprescribing

Aim 4: To assess medication side effects during the study

% reporting any side effects in text

Aim 5: To describe magnitude of changes in quality of life (PROMIS-29) between treatment with tamsulosin and placebo

 change in quality of life measured with PROMIS-29 between treatment with tamsulosin and placebo

9.0 STATISTICAL CONSIDERATIONS

9.1 Power and Sample Size

Sample size justification. We determined sample size based on expected attrition rates. Based on our previously published protocol paper and prior mobile health studies ^{46,47}we expect to fail to meet our study goals (i.e., recruit and retain sufficient participants, achieve sufficient daily questionnaire and N-of-1 trial completion rates, and achieve sufficient "usefulness" scores among participants) at least 10% of the time. Therefore, with a sample size of 20 participants, we will have 90% power to observe at least one failure during this feasibility study. ^{48,49}

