Recruitment Methods	We will use a mix of secure electronic health record messaging and phone calls to invite patients to enroll.
Sample Size	This pilot study will enroll at least 20 older men with LUTS/BPH.
Duration of Study Participation	All study participants will be followed for about 4 months from enrollment (screening/recruitment period, 3-month intervention).

PERSONAL Page 3 of 30

Protocol Version Date: 01/20/2023

List of Abbreviations

5-ARI 5 Alpha-Reductase Inhibitor

AE Adverse Event

AUASI American Urological Association Symptom Index

BPH Benign Prostatic Hyperplasia

CI Confidence Interval

CRC Clinical Research Coordinator

CRF Case Report From

CTCAE Common Terminology Criteria for Adverse Event

EHR Electronic Health Record

HIPAA Health Information Portability and Accountability Act ICD-10 International Classification of Disease, Tenth Revision

ICF Informed Consent Form

IPSS International Prostate Symptom Score

IRB Institutional Review Board

LURN Lower Urinary Tract Dysfunction Research Network

LUTS Lower Urinary Tract Symptoms MPI Multiple Principal Investigator

NIDDK National Institute of Diabetes and Digestive and Kidney Diseases

PCORI Patient Centered Outcomes Research Institute

PHI Protected Health Information

PI Principal Investigator

PSSUQ Post-Study System Usability Questionnaire

RCT Randomized Controlled Trial

rPATD Revised Patients' Attitudes Towards Deprescribing

SAE Serious Adverse Event SD Standard Deviation SOM School of Medicine

UCSF University of California, San Francisco

UTI Urinary Tract Infection

PERSONAL Page 4 of 30

Table of Contents

	ABSTRACT		2
	LIST OF ABBREVIATIONS		4
	TABLE OF CONTENTS		5
1	Introduction		7
1.1	Background: LUTS/BPH	7	•
1.2	Background: Alpha-blocker deprescription		
1.3	Risk/Benefit Assessment		
2	STUDY OBJECTIVES		
3	STUDY DESIGN		
4	SELECTION AND ENROLLMENT OF PARTICIPANTS		11
4.1	Eligibility Criteria	11	
4.2	Recruitment and Screening		
4.3	Participant Registration	12	
5	SCREENING, CONSENT, AND RANDOMIZATION		13
5.1	Screening		
5.2	Informed Consent		
5.3	Randomization and Blinding		
6	STUDY PROCEDURES AND ASSESSMENTS		14
6.1	Schedule of Activities	14	
6.2	Assessments	15	;
6.3	Questionnaire Data15		
6.4	Study Assessments by Visit16		
7	Intervention		18
8	ENDPOINTS		
9	STATISTICAL CONSIDERATIONS	20	
9.1	Power and Sample Size	20	
9.2	Statistical Analysis Plans		
10	ADVERSE EVENTS AND REPORTING REQUIREMENTS		22
10.1	DEFINITIONS		
10.2	EXPECTEDNESS		
10.3	ATTRIBUTION2	2	

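### Twenty participants at a 10% failure rate give an 88% chance of seeing at least one failure, not the 90% stated in Section 9.1

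*Combined protocol and SAP*

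**What the plan says.** Section 9.1 holds the whole sample-size justification. It opens with "We determined sample size based on expected attrition rates". Drawing on earlier work, it then expects the study goals (recruitment and retention, questionnaire and trial completion, usefulness scores) to be missed "at least 10% of the time". From this it concludes, as a direct consequence, that "with a sample size of 20 participants, we will have 90% power to observe at least one failure during this feasibility study". Two references are cited and no formula is shown.

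The synopsis gives the enrolment target as a minimum: "This pilot study will enroll at least 20 older men with LUTS/BPH". Section 3.0 also describes a study of at least 20 men.

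**The concern.** The sentence in Section 9.1 contains everything needed to check it: a number of participants, a failure rate and a probability. The probability does not follow from the other two.

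This is the only operating characteristic the plan states. Section 9.2 promises 95% confidence intervals for the feasibility outcomes but gives no expected width, so a reader who wants to know what 20 men can show has only this figure. As written, it understates the chance that the pilot misses a 10% problem altogether. Sections 1.3 and 13.3 say the aim is to build the evidence for a full-scale efficacy trial, so the figure may be carried into later planning.

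**Working it through.** **Inputs, all from Section 9.1**

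- Number of participants: n = 20 ("with a sample size of 20 participants").
- Failure rate: p = 0.10, the lowest value the text allows ("at least 10% of the time").
- Event: one or more failures among the n participants ("observe at least one failure").
- Stated probability: 0.90.

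No hypothesis test is involved, so no significance level, effect size, standard deviation or drop-out inflation enters.

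**Attempt to reproduce the 90%**

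The plan shows no formula. The natural one treats participants as independent, each failing with probability p:

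P(at least one failure) = 1 − (1 − p)^n = 1 − 0.9^20 = 1 − 0.1216 = **0.8784**

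The Poisson approximation moves further away: 1 − exp(−np) = 1 − exp(−2) = 0.8647. Neither gives 0.90.

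**Size of the gap**

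- Probability: 0.90 − 0.8784 = 0.0216, or 2.2 percentage points.
- Chance of seeing no failure: 12.2% against an implied 10%. The ratio is 12.2/10 = 1.22, about one-fifth higher.

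**Participants needed for 90% at p = 0.10**

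n = ln(1 − 0.90) / ln(1 − 0.10) = ln(0.1) / ln(0.9) = 21.85, so 22.

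| n | P(at least one failure) at p = 0.10 |
|---|---|
| 20 | 87.8% |
| 21 | 89.1% |
| 22 | 90.2% |

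**Failure rate needed for 90% at n = 20**

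p = 1 − 0.1^(1/20) = 0.1087, about 10.9%.

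| p | P(at least one failure) at n = 20 |
|---|---|
| 0.10 | 87.8% |
| 0.105 | 89.1% |
| 0.11 | 90.3% |
| 0.12 | 92.2% |
| 0.15 | 96.1% |
| 0.25 | 1 − 0.75^20 = 99.7% |
| 0.30 | 1 − 0.70^20 = 99.9% |

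**The case against.** The case for leaving the sentence alone has four parts.

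1. **Both inputs are minimums.** The failure rate is at least 10% and enrolment is at least 20. A rate of 10.9%, or 22 men, would deliver 90%, and the wording permits both. This is true. However, a probability promised over a range of inputs has to hold at the bottom of that range, where it is 87.8%. The power sentence itself fixes 20 participants, and nothing commits the study to 22.

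2. **The failure rates the plan worries about are higher.** Section 9.2 calls drop-out of 15–25% acceptable and above 25% inadequate, and Section 8.0 sets a completion goal above 70%. At 15% and beyond, 20 men give 96% or more. This stands, and it limits the practical consequence. It does not correct a statement made at 10%.

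3. **No decision uses the number.** Seeing at least one failure is not a success criterion or a stopping rule. Feasibility is judged by the bands in Section 9.2 and the goals in Section 8.0. The 90% may be no more than a loose rounding of 88%. This also stands: the matter is one of accurate reporting.

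4. **The unit of failure is not defined.** Some listed goals, such as recruiting enough participants, belong to the study and cannot be failed by one man. This is fair, but it does not rescue the 90%: the calculation works only if failure is counted per participant, and on that reading the answer is 88%.

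**Conclusion.** The stated 90% is wrong as written. At 20 participants and a 10% failure rate the probability is 87.8%, which is 2.2 points lower. The inputs fall short of the claim by 2 participants, or by 0.9 points of failure rate.

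The result rests on three assumptions: failure is counted per participant, participants are independent, and the rate sits at the stated floor of 10%. The method is inferred because Section 9.1 shows none.

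The error is minor in size. It deserves correction because it is the plan's sole stated power.

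**What to change.** Replace the final sentence of Section 9.1 with, for example:

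> With 20 participants we will have an 88% probability of observing at least one failure if the per-participant failure rate is 10%.

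This makes explicit the per-participant unit that the calculation needs. The sponsor should confirm that it is the unit intended and say which of the listed goals count as a failure for an individual man.

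If the sponsor prefers to keep 90%, the sentence should name 22 participants, which the existing enrolment wording allows.

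The first option costs one sentence and a slightly less favourable figure. It leaves enrolment, procedures and analysis unchanged.

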We will use descriptive statistics to summarize the feasibility outcomes. In general, frequency distribution and percentage will be used to summarize categorical variables and median with interquartile range (IQR) to describe continuous variables. 95% confidence intervals (CIs) will be used to quantify the precision of these performance estimates.

We will pre-designate drop-out rates of <15%, 15-25%, and >25% as indicating optimal, acceptable, and inadequate participant retention during the 12-week intervention period. Among non-dropouts, we will consider completion of >85%, 75-85%, and <75% of questionnaire completion to indicate optimal, acceptable, and inadequate intervention adherence, respectively.

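### The 90% power in Section 9.1 is the chance of at least one participant-level failure among 20 men (88% at a 10% rate), and one such man is not a missed study goal

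*Combined protocol and SAP*

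**What the plan says.** Section 9.1 is the only justification of the sample size. It opens with "We determined sample size based on expected attrition rates". It then says "we expect to fail to meet our study goals", lists those goals (recruitment and retention, daily questionnaire and N-of-1 trial completion, and usefulness scores), and puts the frequency of failing at "scores among participants) at least 10% of the time". From this it concludes that "with a sample size of 20 participants, we will have 90% power to observe at least one failure during this feasibility study". It does not say what counts as one failure. The abstract gives the size as a minimum: "This pilot study will enroll at least 20 older men with LUTS/BPH".

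The retention goal itself is set elsewhere, as a rate over the whole sample. Section 8.0 (Aim 2) lists "study completion rate (goal >70% of participants" as an endpoint with its target. Section 9.2 states: "We will pre-designate drop-out rates of <15%, 15-25%, and >25% as indicating optimal, acceptable, and inadequate participant retention".

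**The concern.** The goals named in Section 9.1 are properties of the study: enough men recruited, enough retained, completion high enough. A sample either meets such a goal or misses it. The conclusion, by contrast, has the form of a chance of at least one event among 20 people. The event named and the event counted therefore appear to differ in unit. Failure to recruit, for one, cannot occur in a man who is already enrolled.

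The study is meant to prepare a full-scale trial, and retention is one of its stated feasibility outcomes. A reader of Section 9.1 could take it that 20 men will very probably reveal a missed feasibility goal, although the figure given is for an event that Sections 8.0 and 9.2 accept.

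**Working it through.** **Inputs.** n = 20 and a failure rate p of at least 10% (Section 9.1); stated power 90% (Section 9.1); completion goal above 70% (Section 8.0); drop-out tiers below 15%, 15–25% and above 25% (Section 9.2). Assumptions: men drop out independently, and every non-completer counts as a drop-out.

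**1. Reproduce the stated figure.** With each man as a trial, P(at least one failure) = 1 − (1 − p)^n.
- n = 20, p = 0.10: 1 − 0.9^20 = 1 − 0.1216 = 0.878, against 0.90 stated.
- n needed for 90% at p = 0.10: ln(0.1)/ln(0.9) = 21.85, so 22 men (1 − 0.9^22 = 0.902).
- p needed for 90% at n = 20: 1 − 0.1^(1/20) = 0.109.

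**2. Try study-level readings.**
- Goals as the trials, each missed 10% of the time: 1 − 0.9^3 = 0.27, 1 − 0.9^4 = 0.34, 1 − 0.9^5 = 0.41 for three, four or five goals.
- The study as a single trial: the chance of failure is at least 10% by assumption, and n = 20 plays no part.

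Of the readings tried, only the one with 20 men as trials comes near 90%.

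**3. Set one failing man against the retention thresholds.**
- 1 drop-out: 1/20 = 5% drop-out, 95% completion. Goal met; graded optimal.
- 2 drop-outs: 10% drop-out. Still optimal.
- 5 drop-outs: 25% drop-out, 75% completion. Goal met; graded acceptable.
- 6 drop-outs: 30% drop-out, 70% completion. Goal missed (not above 70%); graded inadequate.

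Sections 8.0 and 9.2 thus give the same cutoff with 20 men: 6 or more drop-outs.

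**4. How much one drop-out says about the grade.** At p = 0.10, P(0 to 2 drop-outs) = 0.677. Given at least one drop-out, the chance of an optimal grade is (0.677 − 0.122)/0.878 = 0.63.

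**5. Chance of the inadequate grade.** P(X ≥ 6) for X binomial with n = 20:

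| True drop-out | P(at least 1) | P(6 or more) |
|---|---|---|
| 10% | 0.878 | 0.011 |
| 15% | 0.961 | 0.067 |
| 20% | 0.988 | 0.196 |
| 30% | 0.999 | 0.584 |
| 40% | above 0.999 | 0.874 |

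The two columns answer different questions. Section 9.1 reports the first and describes it in words that fit the second.

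**The case against.** The best defence is that Section 9.1 is loosely worded and not miscalculated. Its opening sentence bases the size on attrition, which points to a per-man rate. The chance of seeing at least one problem is a legitimate thing for a pilot to report. Grading retention is a separate task, which Section 9.2 handles descriptively with confidence intervals and no hypothesis test. The shortfall from 90% to 87.8% is also small, and a rate of at least 10% allows the 10.9% that would close it. All of this stands, and it is why neither the method nor the choice of 20 is at issue. It does not rescue the sentence as written, which attaches the figure to failing the study goals.

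A reader might infer something stronger: that the study has only about a 1% chance of exposing poor retention. The documents do not support that.
- A man-level drop-out of 10% lies in the optimal tier, so a 1% chance of an inadequate grade is a low false-alarm rate and not a weakness.
- Section 9.1 gives 10% as a lower limit, so 1% is a floor.
- The 1% treats the whole 10% as drop-out, although Section 9.1 spreads it over several goals.

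A reader might also extend the point to every goal. That fails too: Section 8.0 gives recruitment in months with no target, no usefulness threshold appears in Sections 8.0 or 9.2, and Section 9.2 does not make clear whether its questionnaire tiers apply per man or to pooled data.

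**Conclusion.** The point holds for retention. The stated 90% is not the probability of the event that Section 9.1 names. It is approximately the probability that at least one of 20 men has a participant-level failure, and at the 10% lower limit that is 87.8%. One drop-out leaves the retention goal met with the best grade; missing the goal takes 6 or more.

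That single men are being counted is inferred from the arithmetic and from the reference to attrition; the text does not say so. The grade probabilities rest on independent drop-out and on equating drop-out with non-completion. At 10%, 15% and 20% true drop-out an inadequate grade would be a false alarm, since those rates are optimal or acceptable under Section 9.2. At 30% and 40% it would be a correct detection, with probability 58% and 87%. A reader might conclude that 20 men are too few; nothing here shows that. The defect lies in what Section 9.1 says the number means.

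**What to change.** In Section 9.1:
- Define the failure as a participant-level event, for example a man who drops out.
- Give the figure as an 88% probability of seeing at least one such man among 20 if the per-man rate is 10%, and drop the description of it as power to observe a failure of the study goals.
- If the section is to speak to the retention goal, add that under independent drop-out the inadequate grade is reached with probability 1%, 7%, 20%, 58% and 87% at true drop-out of 10%, 15%, 20%, 30% and 40%, and note that the 1% is a false-alarm rate.

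The cost is about two sentences and a slightly less favourable headline figure. No extra participants, data or analyses are needed.

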We will use descriptive statistics to summarize the feasibility outcomes. In general, frequency distribution and percentage will be used to summarize categorical variables and median with interquartile range (IQR) to describe continuous variables. 95% confidence intervals (CIs) will be used to quantify the precision of these performance estimates.

We will pre-designate drop-out rates of <15%, 15-25%, and >25% as indicating optimal, acceptable, and inadequate participant retention during the 12-week intervention period. Among non-dropouts, we will consider completion of >85%, 75-85%, and <75% of questionnaire completion to indicate optimal, acceptable, and inadequate intervention adherence, respectively.

10.0 ADVERSE EVENTS AND REPORTING REQUIREMENTS

10.1 Definitions

An adverse event (AE) is any untoward or unfavorable medical occurrence in a study participant, including any abnormal sign (e.g., abnormal physical exam or laboratory finding), symptom, or disease, temporally associated with the participants' involvement in the research, whether or not considered related to participation in the research. Medical conditions or diseases present before starting study interventions should only be considered adverse events if they worsen after starting the interventions.

A serious adverse event (SAE) is any AE that results in death, is life threatening, or places the participant at immediate risk of death from the event as it occurred, requires or prolongs hospitalization, causes persistent or significant disability or incapacity, results in congenital anomalies or birth defects, or any other important event judged by the investigators to jeopardize the safety of a participant based upon appropriate medical judgment.

An unexpected problem is defined as any incident, experience, or outcome that meets all of the following criteria: 1) is unexpected, in terms of nature, severity, or frequency, given the research procedures described in the protocol and the characteristics of the study population; 2) is related or possibly related to participation in the research; and 3) suggests that the research places participants or others at a greater risk of harm (including physical, psychological, economic, or social harm) than was previously known or recognized.

